6.4.1.8 AEs across All Study Phases Combined

Frequency tables of AEs are provided by SOC and PT for the treated analysis set across all safety analysis periods combined for the following endpoints:

- AEs leading to study drug discontinuation

6.4.2 Laboratory Tests

Laboratory tests of clinical interest are collected at the following visits:

- Hematology: Screening, Baseline (Day 1), Day 35, Day 119, Follow-up safety visit (14 days post last dose) and early termination
- Serum chemistry: Screening, Baseline (Day 1), Day 35, Day 119, Follow-up safety visit (14 days post last dose) and early termination. Exceptions are for the following:
 - Liver function Tests (LFTs) (ALT, AST, ALP, TBL, direct bilirubin, indirect bilirubin): All visits except Day 21
 - Lipids (total cholesterol, high-density lipoprotein [HDL] cholesterol, low-density lipoprotein [LDL] cholesterol, triglycerides), folate, HbA1C, P-Amylase or Lipase, TSH, and T4: Screening
- Urinalysis: Screening, Baseline (Day 1), Day 35, Day 119, Follow-up safety visit (14 days post last dose) and early termination.

Laboratory tests of clinical interest for analyses include the following:

- Hematology: hemoglobin, hematocrit, platelets, CBC with differential and absolute neutrophil count
- Serum chemistry: sodium, potassium, chloride, calcium, ALT, AST, LDH, alkaline phosphatase, GGT, phosphorous, bicarbonate, CPK, total protein, albumin, total bilirubin, glucose, creatinine, BUN, uric acid, total cholesterol, LDL, HDL, triglycerides, folate, HbA1C, P-Amylase or Lipase, TSH, and T4
- Urinalysis: macroscopic examination, pH, specific gravity, ketones, nitrites, urobilinogen, leukocyte esterase, protein, glucose, and occult blood.
- LFTs: ALT, AST, TBL and ALP

Refer to the Core SAP for toxicity grading.

Estimated glomerular filtration rate (eGFR) will be derived using the modification of diet in renal disease (MDRD) formula; refer to the Core SAP for additional details.

TLFs will be provided to show data in Systeme Internationale (SI) unit system.

A by-subject listing of the following select laboratory tests will be provided for enrolled subjects with at least one laboratory assessment of grade 3 or 4 abnormality or a positive pregnancy test result: hematology; serum chemistry (including eGFR derived using MDRD); urinalysis. If there is a positive pregnancy test, defined as a serum or urine pregnancy test with either (1) “positive” character value, or (2) numeric value ≥ 25 U/L. The listing will also include all pregnancy test results over time.

In addition, a by-subject listing values and ratios to ULN (i.e., ALT, AST, TBL and ALP) will also be provided for enrolled subjects with select elevations (ALT or AST $> 3 \times$ ULN; ALP or TBL $> 2 \times$ ULN) at any time point. Refer to the Core SAP for listing content.

6.4.2.1 *Laboratory Test Abnormalities*

Frequency tables of laboratory test abnormalities are provided for the following endpoints:

- Worst laboratory test abnormality for each graded laboratory test.
- Laboratory test toxicity grade shift from baseline to the worst toxicity grade for each graded laboratory test

These 2 frequency tables are provided for the following analysis periods and analysis sets:

- On-DBT for the DBT treated analysis set
 - Summarized by rimegepant pooled, placebo pooled, and overall
- On-OL rimegepant for the OL rimegepant treated analysis set
- On-DB or OL rimegepant for the DB or OL rimegepant treated analysis set.

Worst laboratory test abnormality will also be provided for the following analysis periods and analysis sets:

- Follow-up for the follow-up treated analysis set.

6.4.2.2 *LFT Elevations*

Subjects must have non-missing LFT data (i.e., ALT, AST, TBL, or ALP) post-baseline to be included.

Refer to the Core SAP for additional details.

LFT Elevations: Cumulative, Mutually Exclusive, and Composite

Frequency tables of LFT elevations are provided for the following safety analysis periods and analysis sets:

- Pretreatment for the DBT treated analysis set
- On-DBT for the DBT treated analysis set
- On-OL rimegepant for the OL rimegepant treated analysis set
- On-DB or OL rimegepant for the DB or OL rimegepant treated analysis set

- Follow-up for the follow-up treated analysis set.

LFT ULN Shifts from Baseline to Worst Elevation

Frequency tables of LFT ULN shifts from baseline to the worst (highest) LFT elevation are provided for the following safety analysis periods and analysis sets:

- On-DBT for the DBT treated analysis set
 - Summarized by rimegepant pooled, placebo pooled, and overall
- On-DB or OL rimegepant for the DB or OL rimegepant treated analysis set where shifts are based on DB or OL rimegepant baseline.

eDISH Scatter Plots

Evaluation of drug-induced serious hepatotoxicity (eDISH) scatter plots are provided for the following safety analysis periods and analysis sets:

- On-DBT for the DBT treated analysis set with paired ALT and TBL ratios on DBT by treatment group
- On-OL rimegepant for the OL rimegepant treated analysis set with paired ALT and TBL ratios on OL rimegepant
- On-DB or OL rimegepant for the DB or OL rimegepant treated analysis set with paired ALT and TBL ratios on DB or OL rimegepant.

By-Subject Longitudinal LFT Plots

By-subject longitudinal plots will display ratios of values to ULN for AST, ALT, ALP, and TBL (y-axis) versus study day of the laboratory test result (x-axis) for treated subjects with any of the following LFT elevations post-baseline: ALT > 3 x ULN, AST > 3 x ULN, TBL > 2 x ULN, or ALP > 2 x ULN. Each figure also displays additional study milestones (e.g., start of the on-DBT treated analysis period, start of the OL rimegepant safety analysis period, and start of the follow-up period) using vertical lines with their corresponding descriptions in footnotes.

6.4.2.3 *Laboratory Test Changes from Baseline Over Time*

Values and changes from baseline in all hematology and serum chemistry laboratory tests will be summarized using descriptive statistics at each scheduled visit.

The table of values and changes from baseline in hematology and serum chemistry laboratory tests is provided by rimegepant pooled, placebo pooled, and overall for the treated analysis set at the following time points: baseline; Day 35 in the on-DBT safety analysis period; and the 2-week follow-up safety visit.

The table of values and changes from DB or OL rimegepant baseline in all hematology and serum chemistry laboratory tests is provided analogously for the DB or OL rimegepant treated analysis set at the following time points: DB or OL rimegepant baseline; Day 35 in the on-DBT

safety analysis period; each scheduled visit from Day 63 through Day 119 and EOT in the on-OL rimegepant safety analysis period; and the 2-week follow-up safety visit.

Refer to the Core SAP for handling multiple values in an analysis visit window or on the same laboratory collection date, and deriving the EOT value in an on-treatment safety analysis period.

6.4.3 *Vital Signs and Physical Measurements*

Vital signs and physical measurements will be measured at the following visits: Screening, Baseline (Day 1), Day 14, Day 21, Day 35, Day 63, Day 91, Day 119/EOT, and 2-week follow-up safety visit .

Vital signs will include systolic blood pressure, diastolic blood pressure, heart rate, temperature, and respiratory rate. In summaries, only vital signs measured in the sitting position will be included. Physical measurements will include height, weight and BMI.

6.4.3.1 *Vital Signs and Physical Measurements Changes From Baseline Over Time*

Values and changes from baseline in vital sign and physical measurement parameters will be summarized as continuous parameters at each scheduled visit.

The table of values and changes from baseline in vital signs and physical measurements is provided by rimegepant pooled, placebo pooled, and overall for the DBT treated analysis set at the following time points: baseline; each scheduled visit through Day 35 in the on-DBT safety analysis period; 2-week follow-up safety visit.

The table of values and changes from DB or OL rimegepant baseline in vital sign and physical measurement parameters is provided analogously for the DB or OL rimegepant treated analysis set at the following time points: DB or OL rimegepant baseline; each scheduled visit through Day 35 in the on-DBT safety analysis period; each scheduled visit from Day 63 through Day 119 and EOT in the on-OL rimegepant safety analysis period; and 2-week follow-up safety visit.

Refer to the Core SAP for handling multiple values in an analysis visit window or on the same measurement date, and deriving the EOT value in an on-treatment safety analysis period.

6.4.3.2 *Vital Signs and Physical Measurement Abnormalities*

Frequency tables of vital sign and physical measurement abnormalities are provided for the following safety analysis periods and analysis sets:

- On-DBT for the DBT treated analysis set
 - Summarized by rimegepant pooled, placebo pooled, and overall
- On-OL rimegepant for the OL rimegepant treated analysis set using OL rimegepant baseline
- On-DB or OL rimegepant for the DB or OL rimegepant treated analysis set using DB or OL rimegepant baseline

- Follow-up for the follow-up treated analysis set.

6.4.4 *Electrocardiograms*

12-Lead ECGs data will not be analyzed for the CSR.

6.4.5 *Sheehan-Suicidality Tracking Scale (S-STS)*

The S-STS is a prospective rating scale that contains 16 patient-reported questions and 6 clinician-reported questions to track both treatment-emergent suicidal ideation and behaviors. The S-STS will be assessed at early termination and the following visits: Screening, Baseline (Day 1), Day 14, Day 21, Day 35, Day 63, Day 91, Day 119/EOT, and 2-week follow-up safety visit.

S-STS scores are calculated as described in the Core SAP.

Values and changes from baseline in the self-reported S-STS ideation subscale, behavior subscale, and total score will be summarized as continuous parameters at baseline and the worst (highest) score by rimegepant pooled, placebo pooled and overall.

In addition, the number and percentage of subjects in the worst (highest) score change from baseline category (i.e., < -1, -1, no change, 1, > 1) will also be presented by rimegepant pooled, placebo pooled and overall for the ideation subscale, behavior subscale, and total score.

S-STS scores, worst score changes from baseline, and worst score change categories from baseline will be summarized for the following safety analysis periods and populations: (1) on-DBT for treated subjects; (2) on-OL rimegepant for OL rimegepant treated subject; (3) on-DB or OL rimegepant for DB or OL rimegepant treated subjects, using DB or OL rimegepant baseline; and (4) follow-up for follow-up treated subjects.

6.4.6 *Concomitant Procedures*

The by-subject listing of procedures is provided for the enrolled analysis set, and is based on the Concomitant Procedures CRF. Procedures are coded in MedDRA. Refer to the Core SAP for additional details.

6.4.7 *Covid-19 Impact*

Covid-19 impact will not be assessed for this CSR.

6.5 *Pharmacokinetics*

PK will not be analyzed for this CSR.

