**Table 1: Schedule of Assessments Double- Blind Phase**

Procedure	Screening (a) Visit	Baseline (Randomization) (Day 1) (i)	Day 14 (+/- 2 days)	Day 21 (+/- 2 days)	Day 35 (-2/+5 days) (i)
	Visit 1	Visit 2	Visit 3	Visit 4	Visit 5
Informed Consent	X				
Inclusion/Exclusion Criteria	X	X			
Medical History	X				
Neuroimaging (a)	X				
Neurologic Exam	X				
Concomitant Medications and Procedure Review (b)	X	X	X	X	X
Physical Exam	X				X
Vital signs/physical measurements (d)	X	X	X	X	X
Laboratory Assessments	X	X			X
Liver Function Tests	X	X	X		X
Serology (HBsAg, HCV, HIV)	X				
Pregnancy Test (Serum)	X	X			
Pregnancy Test (Urine)		X			X
Urine Drug Screen	X				X
12-Lead ECG	X	X	X		X
Serious Adverse Event Assessment (e)	X	X	X	X	X
Sheehan Suicidality Tracking Scale (S-STS)	X	X	X	X	X
Daily Average Pain (NPRS) (h)	X	X	X	X	X
Patient Global Impression Change Scale (PGI-C)			X	X	X

Procedure	Screening (o) Visit	Baseline (Randomization) (Day 1) (i)	Day 14 (+/- 2 days)	Day 21 (+/- 2 days)	Day 35 (-2/+5 days) (i)
	Visit 1	Visit 2	Visit 3	Visit 4	Visit 5
Pain Disability Index		X	X	X	X
Penn Facial Pain Scale-Revised		X	X	X	X
Record of Daily Rescue Medications		X	X	X	X
Daily Worst Pain (NPRS)	X	X	X	X	X
CCI					
Randomization (c)(g)		X			
Dispense Study Drug/Medication (l)		X	X	X	X (l)
Study Drug/Medication Accountability (f)		X	X	X	X
Paper Diaries Dispensed (m)	X	X			X (m)
Pain Paper Diary returned/reviewed for completeness		X	X	X	X

(a) Subjects must have at least one neuroimaging study (MRI) completed any time prior to randomization. For patients with a strong contraindication to MRI (eg, pacemaker), CT scan, preferably with CTA, will be allowed based on approval by the medical monitor.

(b) Concomitant medications, including standard of care Trigeminal Neuralgia medications, taken during the screening period and rescue medications taken during the double-blind treatment period and open-label extension should be recorded on the subject's paper diary and reviewed by study personnel at each visit.

(c) The actual baseline visit date should be used for IWRS enrollment date.

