3.2.2 Secondary Objective Estimands

Table 2 presents the estimands for secondary objectives.

Table 2: Secondary Objective Estimands

Objective 1	To assess the safety and tolerability of rimegepant relative to placebo in patients with TN
Safety Endpoint	Frequency of unique subjects with: SAEs, AEs leading to discontinuation, AEs judged to be related to study medication, S-STS total score, and clinically significant electrocardiogram (ECG) and laboratory abnormalities observed during the randomization phase of the study
Summary	Using the treated subjects population: 
Number and percentage of subjects with these events or findings
Intercurrent Events	Study drug discontinuation: while-on-treatment strategy for AEs; treatment policy strategy for all other safety endpoints
Objective 2	To evaluate the efficacy of rimegepant vs placebo for improving physical function in TN patients as measured by Penn-FPS-R
Efficacy Endpoint	Change in Penn-FPS-R total score from baseline to the end of the 2-week treatment phase of the study
Summary	Using the mITT population: 
Descriptive statistics for Penn-FPS-R and change from baseline as a continuous variable by treatment group at each visitDifference in mean change from baseline in Penn-FPS-R scores between treatment groups estimated using MMRM
Intercurrent Events	Study drug discontinuation: treatment policy strategy
Objective 3	To evaluate the efficacy of rimegepant vs placebo for improving functional disability in TN patients as measured by the Pain Disability Index
Efficacy Endpoint	Change in Pain Disability Index total score from baseline to the end of the 2-week treatment phase of the study
Summary	Using the mITT population: 
Descriptive statistics for Pain Disability Index and change from baseline as a continuous variable by treatment group at each visitDifference in mean change from baseline in Pain Disability Index between treatment groups estimated using MMRM
Intercurrent Events	Study drug discontinuation: treatment policy strategy
Objective 4	To evaluate the efficacy of rimegepant vs placebo on global functioning as measured by the PGI-C
Outcomes Research Endpoint	PGI-C Scale at the end of the 2-week treatment phase of the study

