7.2 Analysis Periods

Analysis periods are defined as follows:

- Efficacy endpoints
 - On-DBT efficacy: This period is used to assess efficacy during the DBT Phase, and is abbreviated as “DBT” in the efficacy listing.
 - On-OL rimegepant efficacy: This period is abbreviated as “OLRMG” and used only in the efficacy listing.
 - Follow-up efficacy: This period is abbreviated as “FU” and used in the efficacy listing.
- Pretreatment characteristics and safety endpoints
 - Pretreatment: This period is abbreviated as “PRETRT” in listings, and is used to derive baseline values and to assess pretreatment safety endpoints.
 - Pre-OL rimegepant: This period is used to derive the OL rimegepant baseline value.
 - Pre-DB or OL rimegepant: This period is used to derive the DB or OL rimegepant baseline value.
 - On-DBT safety: This period is abbreviated as “DBT” in safety listings, and is used to assess safety endpoints on DBT for the DBT treated analysis set
 - Post-DBT pre-OL rimegepant safety: This period is abbreviated as “INT” in safety listings, and is used to assess safety endpoints during the interim period (i.e., post-DBT pre-OL rimegepant) for the interim treated analysis set.
 - On-OL rimegepant safety: This period is abbreviated as “OLRMG” in safety listings, and is used to assess safety endpoints for the OL rimegepant treated analysis set.
 - On-DB or OL rimegepant safety: This period is used to assess safety endpoints on DB or OL rimegepant treatment for the DB or OL rimegepant treated analysis set
 - Follow-up safety: This period is abbreviated as “FU” in safety listings, and is used to assess safety endpoints during follow-up.
- Outcomes research endpoints
 - DBT outcomes research: This period is abbreviated as “DBT” in outcomes research listings, and used to assess outcomes research endpoints during the DBT Phase
 - OL rimegepant outcomes research: This period is abbreviated as “OLRMG” in outcomes research listings, and used to assess outcomes research endpoints during the OLE Phase.

For endpoints using the “treatment strategy policy”, analysis period 1 is defined as the Day 14 CRF visit, analysis period 2 is defined as the Day 35 or Day 35/ET CRF visit.

For endpoints using the “while-on-treatment strategy”:

- For AEs, refer to Section 6.4.1 for analysis period definitions.

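### Both laboratory change-from-baseline tables omit the Day 14 liver tests, which are half of the planned end-of-period liver values on each treatment

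*SAP*

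**What the plan says.** SAP 6.4.2.3 opens by stating that values and changes in all hematology and serum chemistry tests "will be summarized using descriptive statistics at each scheduled visit". It then specifies two tables:

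- The first, for the treated analysis set, has rimegepant pooled, placebo pooled and overall columns, "at the following time points: baseline; Day 35 in the on-DBT safety analysis period; and the 2-week follow-up safety visit".
- The second, for patients treated with double-blind or open-label rimegepant, is given "at the following time points: DB or OL rimegepant baseline; Day 35 in the on-DBT" phase, followed by every open-label visit from Day 63 to Day 119, end of treatment, and follow-up.

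SAP 6.4.2 gives the liver panel its own collection schedule: "All visits except Day 21". Protocol Table 1 agrees: its row for "Liver Function Tests" is marked at Day 14 and Day 35 but not at Day 21. SAP 6.4.2 lists ALT, AST, ALP and total bilirubin under serum chemistry, so they belong in both tables.

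The matching vital-signs tables in SAP 6.4.3.1 use "each scheduled visit through Day 35 in the on-DBT safety analysis period".

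**The concern.** In this crossover, Day 14 closes period 1 and Day 35 closes period 2. A Day 35-only list suits hematology and the rest of the chemistry panel, which have no other post-baseline double-blind draw. For liver tests it discards one of the two periods.

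This has two consequences:

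- **First table.** SAP 4.2 assesses treated populations by treatment received. At Day 35 the rimegepant column is then made up only of placebo-first patients, and the placebo column only of rimegepant-first patients. The comparison becomes one between sequences within period 2, in a design chosen so that patients act as their own controls. The table has no sequence columns, so the reader cannot see this.
- **Second table.** A rimegepant-first patient's on-drug Day 14 value is missing. The one double-blind value shown comes after washout and a full placebo period.

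Protocol 1.2.3 names change in liver function tests as the main adverse event of interest, so this is the laboratory group for which an incomplete on-treatment mean is least welcome.

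**Working it through.** **Inputs**

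- 60 patients randomized 1:1 to two sequences, so 30 per sequence (SAP 2.2).
- Two 14-day treatment periods separated by a 7-day placebo washout (SAP 2.1).
- Post-baseline double-blind liver draws at Day 14 and Day 35 (SAP 6.4.2; Protocol Table 1).
- 20% dropout (Protocol 9.2; SAP 5).

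**The plan's own figure.** The sample-size statement reproduces. With 60 × 0.8 = 48 evaluable patients, a difference of 2 and a paired SD of 3.8, the noncentrality is (2/3.8) × √48 = 3.65. The two-sided 0.05 paired t-test then has 94.6% power, consistent with the stated value above 90%. Only the 60 patients, the 1:1 ratio and the dropout rate are used below.

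**Planned end-of-period liver values, no dropout**

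| Treatment | Day 14 | Day 35 | Total | Kept by a Day 35-only list |
|---|---|---|---|---|
| Rimegepant | 30 (rimegepant-first) | 30 (placebo-first) | 60 | 30 |
| Placebo | 30 (placebo-first) | 30 (rimegepant-first) | 60 | 30 |

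Omitted share on each treatment: 30/60 = 50%.

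**With 20% dropout**, split evenly by sequence and assuming a dropout gives no Day 35 value, 24 patients per sequence remain at Day 35.

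- All losses before Day 14: 24/(24 + 24) = 24/48 = 50%.
- All losses between Day 14 and Day 35: 30/(30 + 24) = 30/54 = 55.6%.

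**Time off drug at Day 35 for rimegepant-first patients:** 7 days of washout + 14 days of placebo = 21 days.

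**Is the omission deliberate?** Three comparisons suggest it is not.

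1. The opening sentence of 6.4.2.3 covers every scheduled visit, which for liver tests includes Day 14. The table lists contradict it.
2. The second table includes Days 63 and 91. Protocol Table 2 schedules liver tests at those visits but not the general laboratory panel. Liver-only visits are therefore not excluded on principle.
3. The vital-signs tables run through every double-blind visit.

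The likeliest explanation is that the list was written for the general panel and the liver exception was missed.

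**The case against.** The strongest counter-argument is that this is only a wording inconsistency. The opening sentence of 6.4.2.3 already covers Day 14. SAP 3.2.2 assigns "while-on-treatment strategy for AEs; treatment policy strategy for all other safety endpoints", and for treatment-policy endpoints SAP 7.2 says "analysis period 1 is defined as the Day 14 CRF visit". Text elsewhere thus points to including Day 14, and the mock TLF document, which we have not seen, may show it. That is fair evidence of intent, but none of it puts Day 14 into either table. The explicit lists are what a programmer would follow. The Core SAP does not displace them, because this SAP takes precedence where it speaks.

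The second argument is that little depends on it. The safety endpoint counts patients with clinically significant abnormalities. The elevation, grade-shift, ULN-shift and eDISH outputs have no visit limit. This stands, and it is why the point is minor. Those outputs show categories, worst values or scatter, however, and none gives a mean change by treatment.

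Third, the trial stopped early and SAP 1 limits reporting to critical data. The counts above will indeed not be reached. But the SAP kept these tables, and it kept vital signs at every visit.

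Two smaller points also stand. Early-termination laboratory draws are planned, so some dropouts would supply a period 2 value and the 56% would move back towards 50%. And because no liver test is drawn at Day 21, a placebo-first patient's Day 14 value may serve as the rimegepant baseline in the second table. It would still not appear there as an on-rimegepant value, nor should it.

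**Conclusion.** The concern holds, as a minor point. Followed as written, the first table omits half of the planned end-of-period liver values on each treatment: 30 of 60, or 50% to 56% under the stated dropout assumptions. The second table shows no on-drug double-blind liver value for rimegepant-first patients. The single-sequence composition of the pooled columns rests on assigning Day 35 values by treatment received. The counts are planned ones; actual numbers are smaller, but the share stays near half if the sequences are balanced. Only the mean-change display is affected, and detection of marked liver elevations is not lost.

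**What to change.** In SAP 6.4.2.3, add Day 14 for ALT, AST, ALP and bilirubin to both tables.

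- **First table:** form the on-treatment pooled columns by treatment received across the two end-of-period visits. Rimegepant takes Day 14 of rimegepant-first and Day 35 of placebo-first patients; placebo takes the reverse. This follows the period definitions in SAP 7.2 and restores 60 of 60 planned values per treatment.
- **Second table:** show Day 14 as an on-rimegepant value for rimegepant-first patients only, since for placebo-first patients it precedes rimegepant.

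A within-patient rimegepant-minus-placebo difference would be a useful but optional addition. The mock TLFs should be checked for agreement. The cost is one or two lines of SAP wording and a small programming change, with no new data.

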2 STUDY DESCRIPTION

2.1 Study Design

BHV3000-202 is a phase 2, multi-center, double-blind, placebo controlled, crossover trial to assess the safety, tolerability, and efficacy of rimegepant in treating TN in patients who failed to respond adequately to or had intolerance or a contraindication to pharmacotherapy. Current inadequate response to therapy is defined by a daily pain score of greater than or equal to 4 on the “average intensity” on 11-point Numerical Pain Rating Scale (NPRS) during the 14 days prior to baseline. A crossover design with a placebo washout period of 7 days between treatments will be used due to the limited number of subjects, with each patient serving as their own control. The study will be conducted at multiple centers.

Figure 1 displays the study design.

Figure 1: Study Schematic

Prior to randomization, patients will enter a 14 to 30 day screening period during which they will complete daily self-reported assessments of pain intensity over a 24 hour period using an 11 point NPRS, ranging from 0 (for no pain) to 10 (for the worst imaginable pain). Throughout the

study, patients will be allowed to remain on their current medication regimens, provided they have been on a stable dose for a minimum of 4 weeks prior to the randomization visit.

Patients with a mean of ≥ 4 on the daily “average intensity” on the 11 point NPRS, during the last 14 days of the screening period, will be randomized to one of two treatment sequences to receive rimegepant 75 mg immediate release (IR) tablet administered orally vs placebo. Each sequence will include a 2-week treatment phase, with daily dosing of study drug or placebo. This will be followed by a 7-day placebo washout period. After the placebo washout period, another 2-week treatment phase will follow, again with once daily dosing of study drug or placebo. In the first sequence, patients will receive placebo for the first treatment period and rimegepant 75 mg IR tablet during the second treatment period. The second sequence will receive rimegepant 75 mg IR tablet during the first 2 week treatment period, followed by placebo in the second treatment phase.

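### In SAP 6.4.2.3 the Day 35 columns for pooled rimegepant and pooled placebo are a period-2 comparison between sequences, and the table leaves out the Day 14 liver tests

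*SAP*

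**What the plan says.** SAP 6.4.2 gives the sampling visits. For haematology: "Hematology: Screening, Baseline (Day 1), Day 35, Day 119, Follow-up safety visit (14 days post last dose) and early termination". Serum chemistry has the same visits, with exceptions. One exception is the liver group (ALT, AST, ALP and total, direct and indirect bilirubin), taken at "All visits except Day 21" and so also at Day 14. Protocol Table 1 agrees: the full laboratory panel is at Screening, Baseline and Day 35, and liver tests are at those visits and Day 14.

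SAP 6.4.2.3 opens by promising descriptive summaries at every scheduled visit. It then specifies a table for treated subjects, with one column per pooled treatment and one overall, limited to "baseline; Day 35 in the on-DBT safety analysis period; and the 2-week follow-up safety visit". Day 14 is not listed.

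SAP 6.4.2.1 gives the worst-grade and grade-shift tables for the double-blind treated set: "Summarized by rimegepant pooled, placebo pooled, and overall". They are not tied to one visit. SAP 6.4.2.2 admits to the liver-elevation outputs only subjects with non-missing post-baseline liver data. Section 6.4.2.1 states no such condition.

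On treatment order, SAP 2.1 says the rimegepant-first sequence receives "rimegepant 75 mg IR tablet during the first 2 week treatment period, followed by placebo in the second treatment phase". The other sequence receives the reverse.

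**The concern.** In a two-period crossover, a column headed pooled rimegepant tells the reader that on-drug data from both sequences have been combined, and that patients act as their own controls. For the Day 35 laboratory values neither is true. The patients in the placebo column are those given rimegepant in period 1, and any lasting laboratory effect of that exposure would be counted under placebo.

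Clinically significant laboratory abnormalities belong to secondary Objective 1, which assesses safety relative to placebo. Protocol 1.2.3 names liver function tests as the main identified adverse event of interest. A change-from-baseline table that shows liver values from only one sequence on drug therefore discards relevant data that the schedule already collects.

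**Working it through.** **The plan's own figure.** SAP 5 assumes 60 randomised, 20% dropout, a paired-difference SD of 3.8 and a 2-point effect, and states power above 90%. With n = 60 × 0.8 = 48, the exact paired t-test gives 94.6%, so the figure reproduces. The laboratory point does not depend on it; it supplies only the planned number of completers.

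**Schedule against treatment.** Scheduled post-baseline double-blind samples:

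| Test group | Day 14 (end of period 1) | Day 35 (end of period 2) |
|---|---|---|
| Haematology, non-liver chemistry | none | taken |
| ALT, AST, ALP, bilirubin | taken | taken |
| Treatment, placebo-first | placebo | rimegepant |
| Treatment, rimegepant-first | rimegepant | placebo |

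**Assignment to columns.** The SAP text does not say how a Day 35 value is placed in a pooled column. SAP 4.2 assesses treated populations by treatment received, and SAP 7.2 ties Day 14 to period 1 and Day 35 to period 2 for treatment-policy endpoints, which under SAP 3.2 include laboratory tests. On that reading, the rimegepant column at Day 35 is the placebo-first sequence and the placebo column is the rimegepant-first sequence. If pooled instead meant ever treated, every completer would fall in both columns and the table would not separate the treatments.

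**Patients with a scheduled on-rimegepant non-liver panel.** 48 / 2 = 24 (30 of 60 without dropout), all placebo-first.

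**Upper bound with zero events**, one-sided 95%, 1 − 0.05^(1/n):
- n = 24: 1 − 0.05^(1/24) = 11.7%
- n = 48: 1 − 0.05^(1/48) = 6.1%

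**Precision of the Day 35 contrast**, with sd the SD of one laboratory value. Between sequences, SE = sd × √(2/24) = 0.289 sd. A contrast using both periods would have SE = sd × √(2(1 − ρ)/48). The variance ratio is 2/(1 − ρ), which is 2.0, 2.5, 4 and 10 for ρ = 0, 0.2, 0.5 and 0.8. The documents give no correlation for laboratory values, so this range is an assumption.

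**Denominator in 6.4.2.1 (conditional).** Let p be the on-drug rate of a non-liver abnormality. Sampled patients yield 24p events. Divided by the 24 sampled, the rate is p. Divided by all 48 exposed to rimegepant in either period, it is 24p/48 = p/2.

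**Internal comparison.** The corresponding vital-signs table in SAP 6.4.3.1 takes every scheduled visit through Day 35. The laboratory table does not, although liver tests have a scheduled Day 14 visit.

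**The case against.** The strongest reply is that the main laboratory risk is covered. Liver tests are drawn on rimegepant in both sequences, and the Day 14 values can enter the worst-grade, shift, liver-elevation and eDISH outputs, none of which is restricted to Day 35. That stands. A reader might infer that all chemistry, or every pooled laboratory table, lacks on-drug data from rimegepant-first patients; the documents do not support that.

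A reader might also infer that abnormality percentages will be halved. This too goes beyond the documents. Section 6.4.2.3 holds continuous summaries, with n displayed and no percentages. For 6.4.2.1, counting rules are referred to the Core SAP, which is not available here, and the one explicit rule in this SAP (6.4.2.2) already requires non-missing data. Halving is therefore a conditional risk for non-liver tests only.

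Other on-drug data from rimegepant-first patients may exist: early-termination samples, repeat laboratory tests, local laboratory tests at remote Day 14 or Day 21 visits (panel unspecified), and open-label Day 119 panels. Clinically significant results are also captured as adverse events, which the SAP assigns to a period. These soften the point, but do not make the Day 35 columns pooled.

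Finally, SAP 5 says significance will not be evaluated, and SAP 1 says the study was terminated in 1Q2023 with only critical data to be analysed. The tables are descriptive and the stakes are modest. Adding a full panel at Day 14 is moot, because the study has ended.

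**Conclusion.** The point holds in a limited form. For haematology and non-liver chemistry, early-termination, unscheduled and local samples aside, the Day 35 columns compare placebo-first patients on rimegepant with rimegepant-first patients now on placebo. The same is true of the liver rows in that table, because the Day 14 liver values are omitted despite the promise to summarise each scheduled visit.

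In size, about 24 rather than 48 planned completers supply a scheduled on-rimegepant non-liver panel. This rests on 60 randomised, equal allocation and 20% dropout. The actual number is smaller, so the actual bounds are wider. Relabelling does not recover that information; it stops the heading from overstating it. The possible understatement of non-liver percentages in 6.4.2.1, by up to about half, depends on a counting rule that cannot be seen here. The column reading rests on assignment by treatment taken in the period, which the SAP implies but does not state.

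**What to change.** Amend the SAP in three places:

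1. In 6.4.2.3, add Day 14 as a time point for the liver tests, with each value assigned to the treatment taken in that period.
2. In 6.4.2.3, label the Day 35 columns, for all tests including liver tests, as period 2 only and between sequences.
3. In 6.4.2.1, extend the condition already used in 6.4.2.2: each treatment's denominator counts only subjects with a post-baseline result for that test on that treatment. If the Core SAP already requires this, a cross-reference is enough.

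The cost is SAP wording, table labels and minor programming on data already scheduled for collection. No change to the sampling schedule is proposed.
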